For patients who do not tolerate APR-246 initial dosing schedule, dose adjustment is permitted in order to allow the patient to continue on study drug. In general, doses should not be reduced

for grade 1 toxicities or grade 2 toxicities with resolution on dose interruption (see Table 8), but treatment to control symptoms should be provided as appropriate. The starting dose level of APR-246 will be based on the recommended phase 2 dose (RP2D) upon completion of the phase 1 component of the trial (see Table 5). If dose level 3 (i.e. 100mg/kg LBW) is the RP2D based on the phase 1b part of the trial, the dosing will be changed to an equivalent fixed dose regimen of 4500mg/patient. For each patient, a maximum of 2 dose reductions of APR-246 (as outlined in Table 7) will be allowed. Patients requiring an additional dose reduction will be discontinued from treatment with APR-246. Patients whose treatment is interrupted or permanently discontinued due to an adverse event or clinically significant laboratory value must be followed up within 30 days, or resolution of the AE to \leq grade 1, whichever occurs first, that includes all study assessments appropriate to monitor the event.

Table 7 Dose reduction steps for APR-246 (Phase 2 only)

APR-246 dose levels and dose reduction*	
Starting dose level	RP2D days 1-4 of each cycle
Dose level – 1	RP2D-500mg fixed dose days 1-4 of each cycle**
Dose level – 2	RP2D-1000mg fixed dose days 1-4 of each cycle**

*Dose reduction should be based on the worst preceding toxicity.
 ** = If a dose reduction below dose level –2 is required, the patient should be permanently discontinued from APR-246

Guidelines for dose modification and dose interruption for toxicities suspected to be related to APR-246 are described in Table 8.

Table 8 APR-246 – recommended dose modifications and criteria for treatment interruption and re-initiation with treatment-related adverse events

These changes must be recorded on the Dosage Administration Record CRF.

Worst toxicity (CTCAE 4.03 Grade)**	Dose Modifications for APR-246
HEMATOLOGICAL (only applicable for patients with normal baseline absolute neutrophil count (ANC) and platelets)	
Neutropenia (ANC)	
Severe Febrile neutropenia	Omit dose until resolved, then ↓ 1 dose level

Worst toxicity (CTCAE 4.03 Grade)**	Dose Modifications for APR-246
(ANC < 0.5 x 10 ⁹ /L, temperature of ≥ 38 °C and ICU admission)	
Thrombocytopenia	

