Grade 4 (PLT < 25 x 10 ⁹ /L) AND major bleeding event	Permanently discontinue patient from APR-246
RENAL	
Serum creatinine	
Grade 1 (< 2 x ULN)	Maintain dose level
Grade 2 (2 – 3 x ULN)	Omit dose until resolved to ≤ grade 1, then: If resolved in ≤ 7 days, then maintain dose level If resolved in > 7 days, then ↓ 1 dose level
Grade 3 (> 3.0 – 6.0 x ULN)	If resolved in ≤ 7 days, then ↓ 1 dose level If resolved in > 7 days, discontinue patient from APR-246
Grade 4 (> 6.0 x ULN)	Permanently discontinue patient from APR-246
HEPATIC	
Bilirubin	
(*for patients with Gilbert Syndrome, these dose modifications apply to changes in direct bilirubin only) will be fractionated if elevated	
Grade 1 (> ULN - 1.5 x ULN)	Maintain dose level with LFTs* monitored as per protocol
Grade 2 (> 1.5 - 3.0 x ULN) with ALT or AST ≤ 3.0 x ULN	Omit dose until resolved to ≤ Grade 1, then: If resolved in ≤ 7 days, then maintain dose level If resolved in > 7 days, then ↓ 1 dose level
Grade 3 (> 3.0 - 10.0 x ULN) with ALT or AST ≤ 3.0 x ULN	Omit dose until resolved to ≤ Grade 1, then: If resolved in ≤ 7 days, ↓ 1 dose level If resolved in > 7 days, discontinue patient from APR-246
Grade 4 (> 10.0 x ULN)	Permanently discontinue patient from APR-246
AST or ALT	
Grade 1 (> ULN – 3.0 x ULN)	Maintain dose level with LFTs* monitored per protocol
Grade 2 (> 3.0 - 5.0 x ULN) without total bilirubin elevation to > 2.0 x ULN	Omit dose until resolved to ≤ Grade 1, then If resolved in ≤ 7 days, then maintain dose level If resolved in > 7 days, then ↓ 1 dose level
Grade 3 (> 5.0 - 20.0 x ULN) without total bilirubin elevation to > 2.0 x ULN	Omit dose until resolved to ≤ Grade 1, then If resolved in ≤ 7 days, then maintain dose level If resolved in > 7 days, then ↓ 1 dose level

Worst toxicity (CTCAE 4.03 Grade)**	Dose Modifications for APR-246
Grade 4 (> 20.0 x ULN) without bilirubin elevation to > 2.0 x ULN	Permanently discontinue patient from APR-246
*(LFTs include albumin, ALT, AST, total bilirubin (fractionated if total bilirubin > 2.0 x ULN), alkaline phosphatase.	
CNS – dizziness, dyskinesia and ataxia	
Grade 1	Maintain dose level
Grade 2	If resolved with medical therapy (e.g., prochlorperazine or antihistamines), continue same dose level If not resolved despite treatment interruption and maximal medical therapy, stop infusion and ↓ 1 dose level for subsequent dose

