Grade 3	If resolved with medical therapy (e.g., prochlorperazine or antihistamines), continue same dose level If not resolved despite treatment interruption and maximal medical therapy, stop infusion and ↓ 1 dose level for subsequent dose
Grade 4	Permanently discontinue patient from APR-246.
Infusion Related Reaction	
Grade 1	Maintain dose level.
Grade 2	Maintain dose level; Symptomatic management (e.g., antihistamines, corticosteroids, narcotics, IV fluids)
Grade 3	If resolved in < 4 hours with treatment interruption and medical therapy (e.g., antihistamines, corticosteroids, narcotics, IV fluids), continue same dose level and rate. If not resolved in < 4 hours despite treatment interruption and maximal medical therapy, stop infusion and ↓ 1 dose level for subsequent dose
Grade 4	Permanently discontinue patient from APR-246.
Nausea/Vomiting/Diarrhea	
Grade 1	Maintain dose level
Grade 2	If resolved, then maintain dose level If not resolved despite maximal medical therapy, then ↓ 1 dose level
Grade 3	If resolved, then maintain dose level If not resolved despite maximal medical therapy, then ↓ 1 dose level
Grade 4	Permanently discontinue patient from APR-246

Worst toxicity (CTCAE 4.03 Grade)**	Dose Modifications for APR-246
QTc Prolongation	
Grade 1	Maintain dose level
Grade 2	Correct electrolytes and discontinue concomitant medications that cause QTc prolongation. If resolved, then maintain dose level. If not resolved, then ↓ 1 dose level
Grade 3	Omit dose until resolved to ≤ Grade 1, If resolved, then ↓ 1 dose level If not resolved despite correction of electrolytes and discontinuation of concomitant medications that cause QTc prolongation, permanently discontinue maximal medical therapy
Grade 4	Permanently discontinue patient from APR-246
** Common Terminology Criteria for Adverse Events (CTCAE) version 4.03. These changes must be recorded on the Dosage Administration Record eCRF.	

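### The grade 3 QTc row of Table 8 orders supportive therapy, not APR-246, to be stopped, so some patients who should come off the drug could be restarted one dose level lower

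*Combined protocol and SAP*

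**What the plan says.** Section 10.5 of the protocol covers APR-246 dose modification in Phase 2. Its Table 8 is titled as "recommended dose modifications and criteria for treatment interruption and re-initiation with treatment-related adverse events", and the action column is headed "Dose Modifications for APR-246".

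The grade 3 QTc cell has three parts. It opens with a hold and a condition for resuming: "Omit dose until resolved to ≤ Grade 1, If resolved", after which the dose drops one level. It then takes the case where prolongation persists although electrolytes have been corrected and QT-prolonging concomitant drugs stopped. For that case the order is "permanently discontinue maximal medical therapy".

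The neighbouring QTc rows differ. The unresolved branch at grade 2 reads "If not resolved, then ↓ 1 dose level", and grade 4 reads "Permanently discontinue patient from APR-246".

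Outside the table, Section 10.3 makes permanent discontinuation of study drug mandatory once a dose delay passes 28 days. Section 9.c requires treatment to stop if the investigator judges an adverse experience to make continued participation an unacceptable risk.

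**The concern.** The object of the verb is wrong. In a column about APR-246, the clause for unresolved grade 3 QTc prolongation stops medical therapy. Taken at face value it removes supportive care from a patient whose QTc is still prolonged and does not say that APR-246 ends.

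The protocol treats QTc as a safety matter. Section 4.1 excludes patients with QTc of 470 msec or more. Section 13 schedules EKGs on day 1 and at the end of infusion on day 4 of cycle 1, then at the day 1 evaluation of each later cycle. Section 2.5.2 reports that the ovarian study was still collecting QTc data at 100 mg/kg lean body mass, the basis from which the Phase 2 fixed dose of 4500 mg is derived. In a multi-institution trial, a cardiac stopping rule should give every site the same answer without requiring it to guess the intent.

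**Working it through.** No published figure has to be reproduced. The check compares wording within Table 8 and then follows patients through the rules as written.

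**1. The QTc branches.**

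| Grade and branch | Final instruction on APR-246 |
|---|---|
| 1 | maintain |
| 2, resolved | maintain |
| 2, not resolved | reduce one level |
| 3, resolved | reduce one level |
| 3, not resolved | none beyond the opening hold |
| 4 | permanently discontinue |

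Five of six branches state a final disposition for APR-246. The sixth leaves only the temporary hold.

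**2. Permanent-discontinuation orders in Table 8.** Orders naming APR-246 are at grade 4 for thrombocytopenia with major bleeding, creatinine, bilirubin, AST/ALT, CNS, infusion reaction, nausea/vomiting/diarrhea and QTc, which makes 8. The grade 3 QTc clause is the only one that does not, so 8 of 9 name the drug. The grade 3 creatinine and bilirubin rows also use "If resolved in > 7 days, discontinue patient from APR-246". Adding those two gives 8 + 2 = 10 of 9 + 2 = 11.

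**3. Uses of the phrase maximal medical therapy.** It appears in CNS grades 2 and 3, infusion reaction grade 3, and nausea/vomiting/diarrhea grades 2 and 3. In all five it belongs to the condition, as in "If not resolved despite maximal medical therapy, then": treatment that has been tried and has failed. The grade 3 QTc clause is the sixth use and the only one where the phrase is the thing to be stopped.

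Both counts point to a slip. The sentence runs on with no gap or redaction mark, so a PDF reading fault is unlikely.

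**4. Three patients with grade 3 QTc prolongation, under the text as written.**

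- *Patient A: QTc responds to corrective measures.* The dose is held and then reduced one level. The rule works.
- *Patient B: QTc never returns to grade 1 or lower.* The hold has no end, and once the delay exceeds 28 days Section 10.3 requires permanent discontinuation. The patient comes off APR-246 despite the faulty clause.
- *Patient C: corrective measures fail, but QTc falls to grade 1 or lower within 28 days while the drug is held.* A permanent-discontinuation branch would evidently be meant to keep this patient off the drug. As written, the only usable instruction left is the resolved branch, which is to restart one level down. The 28-day rule is not triggered. Section 10.3's general text on grade 3 events favours dose reduction in most instances and refers back to the tables.

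**5. What the difference means for Patient C.** If the fixed 4500 mg regimen is in use, Table 7 puts one level down at 4500 − 500 = 4000 mg per day. Over days 1–4 that is 4 × 4000 = 16,000 mg per cycle, against 0 mg under permanent discontinuation.

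**The case against.** The best defence is that the protocol already takes the patient off the drug. The cell begins with a hold, the hold has no end while QTc stays above grade 1, and Section 10.3 turns it into mandatory discontinuation after 28 days. The Section 9.c criterion adds investigator judgment, and the day 1 EKGs help to catch persistent prolongation before redosing. Table 8 describes its contents as recommendations, while the binding language is in Sections 9.c and 10.3. Nor is this the only row that leans on the general rule: bilirubin grade 2 and AST/ALT grades 2 and 3 have branches only for toxicity that resolves within or after 7 days, and none for toxicity that never resolves.

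Most of this stands. A reader might infer from the faulty clause that a patient with unresolved grade 3 QTc prolongation may stay on APR-246, or that nothing in the protocol removes that patient. The documents do not support that reading, because the hold and the 28-day rule together give a written, mandatory way off the drug.

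The defence does not reach Patient C. The hold is temporary, the delay rule does not apply at 28 days or less, and the unacceptable-risk criterion is discretionary. The bilirubin and AST/ALT rows are silent on non-resolution. The QTc row is not: it has a permanent-discontinuation branch and names the wrong thing to discontinue.

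The text after the heading on QT-prolonging agents in Section 6.c is redacted, so QT-specific guidance there cannot be ruled out. It would not change the wording of this cell.

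**Conclusion.** The clause is wrong as written and should be corrected, but the exposure is narrow. It concerns Phase 2 patients with grade 3 QTc prolongation in whom electrolyte correction and withdrawal of QT-prolonging drugs fail, and whose QTc then falls to grade 1 or lower within 28 days. They could be restarted one dose level lower when the table's pattern points to permanent discontinuation. Separately, the literal text tells sites to stop supportive therapy, although most investigators would probably see what was meant.

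The number of patients affected cannot be stated, because the visible text gives no rate of grade 3 QTc events.

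The conclusion rests on two assumptions. The first is that the intended object was APR-246, which the column heading and the 8-of-9 pattern support but only the clinical team can confirm. The second is that a site can judge prolongation unresolved before 28 days have passed. The cell sets no time limit, so the size of this group depends on when sites make that call.

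Nothing here affects the endpoints, the Simon two-stage design or the CR analysis.

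**What to change.** In the grade 3 QTc cell of Table 8, leave the condition as it is (electrolyte correction and withdrawal of QT-prolonging concomitant drugs) and replace "permanently discontinue maximal medical therapy" with the wording of the grade 4 row, "Permanently discontinue patient from APR-246". The clinical team should confirm that this was the intent.

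Do not move the phrase about maximal medical therapy into the condition. The protocol does not define it for QTc, and a third requirement could delay stopping the drug.

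The cost is one table cell in an amendment, with no change to sample size, endpoints or analysis.

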11. ADVERSE EVENTS: REPORTING REQUIREMENTS

All SAEs should be reported to the principal investigator at H. Lee Moffitt Cancer Center as well as the clinical research coordinator immediately. All SAEs must also be reported within 24 hours of being known to Aprea. These toxicities will be reviewed by the principal investigator and appropriate measures taken in terms of delaying or reducing or omitting the next cycle of therapy. Any SAE occurring from the time of administration of the first dose of study drug until 30 days after the final dose of study drug must be promptly reported to Aprea via fax on a redacted copy of the Oncore database SAE form. Any SAE occurring after this time that is thought to be possibly related to prior treatment with study drug should also be reported and recorded on the AE log. SAEs must be followed until resolution or deemed irreversible. All relevant follow-up information must be promptly reported and recorded in the Oncore database.

a. Definition of an AE

Any untoward medical occurrence in a subject or clinical investigation subject, temporally associated with the use of a medicinal product, whether or not considered related to the medicinal product. Note: An AE can therefore be any unfavorable and unintended sign (including an abnormal laboratory finding), symptom, or disease (new or exacerbated)

temporally associated with the use of a medicinal product. Events meeting the definition of an AE include:

- Exacerbation of a chronic or intermittent pre-existing condition including either an increase in frequency and/or intensity of the condition.
- New conditions detected or diagnosed after investigational product administration even though it may have been present prior to the start of the study.
- Signs, symptoms, or the clinical sequelae of a suspected interaction
- Signs, symptoms, or the clinical sequelae of a suspected overdose of either investigational product or a concomitant medication (overdose per se will not be reported as an AE/SAE). “Lack of efficacy” or “failure of expected pharmacological action” per se within the duration of initial APR-246 treatment/exposure of 6 cycles will not be reported as an AE or SAE. However, the signs and symptoms and/or clinical sequelae resulting from lack of efficacy will be reported if they fulfill the definition of an AE or SAE.
- Stop dates for AEs can be either the last date that the AE occurred, or the next date which reflects a change in grade/status.

Events that **do not** meet the definition of an AE include:

- Medical or surgical procedure (e.g., endoscopy, appendectomy); the condition that leads to the procedure is either an AE or (if existing pre-study) a baseline medical history item.
- Situations where an untoward medical occurrence did not occur (social and/or convenience admission to a hospital. Example: Hospital admission for sole purpose of red blood cell transfusion).
- Anticipated day-to-day fluctuations of pre-existing disease(s) or condition(s) present or detected at the start of the study that do not worsen.
- Signs/symptoms of Gr. 1 or Gr. 2 expected side effects of Azacitidine, as noted in visit notes by treating MD and/or designated staff. This includes (for example, but not limited to) Gr. 1-2: Nausea, constipation, injection site reactions, decreased neutrophil count, decreased platelet count. Must be located in source document that items are specifically attributable to Azacitidine.

- Signs/symptoms of Gr. 1 or Gr. 2 expected side effects of red blood cell and/or platelet transfusion needs. This includes (for example, but not limited to) Gr. 1-2: dizziness, headache, hypotension, hypertension, dyspnea, muscle weakness, ataxia, fall, petechiae, bruising. Must be located in source document that items are specifically attributable to the need for red blood cell transfusion and/or platelet transfusion.
- Items which are transient (example: seasonal allergies; joint pain during thunderstorms) will be listed as baseline medical history items and are not considered new AEs if only occurring during certain times of year or with certain events if ongoing chronically, and do not increase in grade and are not attributable to study medication.

b. Serious Adverse Event (SAE) Definition

A serious adverse event is one that at any dose (including overdose):

- Results in death
- Is life-threatening
- Requires inpatient hospitalization or prolongation of existing hospitalization
- Results in persistent or significant disability or incapacity
- Is a congenital anomaly or birth defect
- Is an important medical event
- Suspected positive pregnancy

NOTE: The term “life-threatening” the definition refers to an event in which the subject was at risk of death at the time of the event. It does not refer to an event, which hypothetically might have caused death, if it were more severe.

- Requires hospitalization or prolongation of existing hospitalization. NOTE: In general, hospitalization signifies that the subject has been detained (usually involving at least an overnight stay) at the hospital or emergency ward for observation and/or treatment that would not have been appropriate in the physician’s office or out-patient setting. Complications that occur during hospitalization are AEs. If a complication prolongs hospitalization or fulfills any other serious criteria, the event is serious. When in doubt as to whether “hospitalization” occurred or was necessary, the AE should be considered serious. Hospitalization for elective treatment of a pre-existing condition that did not worsen from baseline is not considered an AE.
- Results in disability/incapacity

NOTE: The term disability means a substantial disruption of a person's ability to conduct normal life functions. This definition is not intended to include experiences of relatively minor medical significance such as uncomplicated headache, nausea, vomiting, diarrhea, influenza, and accidental trauma (e.g., sprained ankle) which may interfere or prevent everyday life functions but do not constitute a substantial disruption.

- All treatment related grade 4 non-hematologic laboratory abnormalities assessed using the National Cancer Institute (NCI) Common Terminology Criteria for Adverse Events (CTCAE) v 4.03.

Medical or scientific judgment should be exercised in deciding whether reporting is appropriate in other situations, such as important medical events that may not be immediately life-threatening or result in death or hospitalization but may jeopardize the subject or may require medical or surgical intervention to prevent one of the other outcomes listed in the above definition. These should also be considered serious. Examples of such events are invasive or malignant cancers, intensive treatment in an emergency room or at home for allergic bronchospasm, or convulsions that do not result in hospitalization, or development of drug dependency or drug abuse.

c. Relationship to Investigational Product

It is a regulatory requirement for investigators to assess relationship to investigational product based on information available. The assessment should be reviewed on receipt of any new information and amended if necessary. "A reasonable possibility" is meant to convey that there are facts/evidence or arguments to suggest a causal relationship. Facts/evidence or arguments that may support "a reasonable possibility" include, e.g., a temporal relationship, a pharmacologically-predicted event, or positive dechallenge or rechallenge. Confounding factors, such as concomitant medication, a concurrent illness, or relevant medical history, should also be considered.

d. Laboratory and Other Safety Assessment Abnormalities Reported as AEs and SAEs

Any abnormal laboratory test results (hematology, clinical chemistry, or urinalysis) or other safety assessments (e.g., ECGs, vital signs measurements), including those that worsen from baseline should be recorded as per the NCI-CTCAE 4.03 criteria. However, these laboratory results are to be recorded as AEs or SAEs if deemed clinically significant in the medical and scientific judgment of the investigator or treating physician. Any clinically significant safety

assessments that are associated with the underlying disease are **not** to be reported as AEs or SAEs, except for findings judged by the investigator or treating physician to be more severe than expected for the subject's condition or death. Data will be collected for typical disease-related events such as anemia, leukopenia or worsening of thrombocytopenia. All infections experienced during the study are to be recorded as AEs or SAEs.

e. Disease-Related Events and/or Disease-Related Outcomes Not Qualifying as SAEs

During the study period, the following conditions will not qualify as an AE or SAE provided they are not considered attributable to study medication:

- Events that occur prior to the 1st dose of APR-246.
- Cases of disease progression.

f. Pregnancy

Any pregnancy that occurs during study participation must be reported. To ensure subject safety, each pregnancy must be reported to the FDA with CC notification to Aprea within 2 weeks of learning of its occurrence. The pregnancy must be followed up to determine outcome (including premature termination) and status of mother and child. Pregnancy complications and elective terminations for medical reasons must be reported as an AE or SAE. Spontaneous abortions must be reported as an SAE. Any SAE occurring in association with a pregnancy, brought to the investigator's attention after the subject has completed the study and considered by the investigator as possibly related to the investigational product, must be promptly reported to the pharmacovigilance groups at the H. Lee Moffitt Cancer Center and Aprea. In addition, the investigator must attempt to collect pregnancy information on any female partners of male study subjects who become pregnant while the subject is enrolled in the study. Pregnancy information must be reported to the H. Lee Moffitt Cancer Center as described above.

g. Prompt Reporting of Serious Adverse Events and Other Events to Aprea

The investigator must inform Aprea of any SAE within 24 hours of being aware of the event. This must be documented in Oncore, printed, signed, dated and emailed to Aprea via Theradex at: [contact]. This form must be completed and supplied to Aprea within 24 hours/1 business day. The initial report must be as complete as possible, including an assessment of the causal relationship between the event and the investigational product, if available.

Information not available at the time of the initial report must be documented in Oncore as a follow up SAE (also printed, signed, dated and emailed to Aprea via Theradex at: [contact] . If the SAE is deemed reportable to the FDA, then a MedWatch will also need to be completed and sent to Moffitt Cancer Center for review (see IND section 17.5 for further details) and FDA submission.

A final report to document resolution of the SAE is required. Any serious adverse events which occur during the clinical study or within 30 days of receiving the last dose of study medication, whether or not related to the study drug, must be reported by the investigator. In addition, any SAEs which occur as a result of protocol specific diagnostic procedures or interventions must also be reported. SAEs brought to the attention of the investigator at any time after cessation of APR-246 and considered by the investigator to be related or possibly related to APR-246 must be reported to Aprea with subsequent to the FDA if and when they occur. Additionally, in order to fulfill international reporting obligations, SAEs that are related to study participation (e.g., procedures, invasive tests, and/or change from existing therapy) or are related to a concurrent medication will be collected and recorded from the time the subject consents to participate in the study until he/she is discharged.

Type of Event	Initial Reports		Follow-up Information on a Previous Report	
	Time Frame	Documents	Time Frame	Documents
All SAEs	24 hours*	“SAE” data collection tool	24 hours*	Updated “SAE” data collection tool
Pregnancy	2 Weeks*	Pregnancy Notification Form	2 Weeks*	Pregnancy Follow-up Form

*From the time point when the SAE or pregnancy became known to reporter.

h. Regulatory Reporting Requirements for SAEs

Prompt notification of SAEs by the investigator to Aprea is essential so that legal obligations and ethical responsibilities towards the safety of subjects are met. The sponsor-investigator has a legal responsibility to notify both the local regulatory authority and other regulatory agencies about the safety of a product under clinical investigation. The sponsor-investigator will comply with specific regulatory requirements relating to safety reporting to the regulatory

authority/Institutional Review Board (IRB), the FDA, notification to Aprea, and sub-investigators. Investigator safety reports are prepared for suspected unexpected serious adverse reactions according to local regulatory requirements and those policies set forth by the FDA and are forwarded to investigators and Aprea as necessary. An investigator who receives an investigator safety report describing an SAE(s) or other specific safety information (e.g., summary or listing of SAEs) from the H. Lee Moffitt Cancer Center will file it with the CIB and will notify the IEC /IRB, if appropriate according to local requirements.

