10. DOSING DELAYS/MODIFICATIONS

1. Dose modification and dose delay

For patients who do not tolerate the protocol-specified dosing schedule, dose adjustments are permitted in order to allow the patient to continue the study treatment. All dose modifications, interruptions or discontinuations must be based on the worst preceding toxicity as graded by the

NCI Clinical Toxicity Criteria (NCI-CTCAE version 4.03). Once a dose has been reduced during a treatment cycle, re-escalation will not be permitted during any subsequent cycle (with exception of CNS events, see 10.2). If the administration of APR-246 is interrupted for reasons other than toxicity, then treatment with the respective study drug may be resumed at the same dose. The same provision applies if the patient experienced an unacceptable toxicity not specifically described in Table 8 provided that this toxicity resolved to \leq CTCAE grade 1, unless otherwise specified.

2. Treatment of adverse events of the CNS related to APR-246

If a patient reports any clinical adverse event of any grade during the administration period of APR-246 that could be considered to originate from the central nervous system (e.g., dizziness, vertigo, nausea) then the following medications may be used (Table 6). Prochlorperazine is not required to be taken at any point but is per discretion of the treating physician.

Table 6. Adjuvant Medications for use with APR-246

Indication	Supportive Measure
Central Nervous System (CNS) symptoms (Treatment and Prevention)	Prochlorperazine 10 mg orally tid as needed Start Day -1 prior to APR-246 administration
Persistent CNS symptoms	Diphenhydramine 50 mg IV (or similar anti-histamine)

Prochlorperazine 10 mg orally tid (three times daily) to continue until end of Day 4 of the cycle. When used prophylactically for future treatment, start the day prior to Day 1 administration of APR-246. If during the infusion the patient continues to remain symptomatic, intravenous administration of diphenhydramine 50 mg (or similar anti-histamine) should be considered. If prophylactic prochlorperazine results in \leq grade 1 CNS toxicity on subsequent doses, re-escalation to previous dose level can occur with the next cycle at the discretion of the study investigator.

3. Treatment interruption and treatment discontinuation

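### Grade 1-2 nausea, dizziness or ataxia charted to azacitidine or transfusion need is not counted as an AE, so low-grade toxicity of the combination is under-counted

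*Combined protocol and SAP*

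**What the plan says.** Section 11.a opens with a broad definition: an untoward occurrence counts as an AE "whether or not considered related to the medicinal product". It then lists events that fall outside the definition. Two of the entries work by attribution:

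- **Azacitidine.** "Signs/symptoms of Gr. 1 or Gr. 2 expected side effects of Azacitidine, as noted in visit notes by treating MD and/or designated staff". The examples are "Nausea, constipation, injection site reactions, decreased neutrophil count, decreased platelet count".
- **Transfusion need.** "Signs/symptoms of Gr. 1 or Gr. 2 expected side effects of red blood cell and/or platelet transfusion needs". The examples are "dizziness, headache, hypotension, hypertension, dyspnea, muscle weakness, ataxia, fall, petechiae, bruising".

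Both lists are open-ended. Both carry a condition; for azacitidine it reads "Must be located in source document that items are specifically attributable to Azacitidine", and a parallel sentence covers transfusion need.

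Elsewhere the protocol treats some of the same terms as toxicities of APR-246. Section 10.2 deals with events of any grade during APR-246 administration that could "originate from the central nervous system (e.g., dizziness, vertigo, nausea"). Table 8 has an APR-246 row headed "CNS – dizziness, dyskinesia and ataxia" and another for nausea, vomiting and diarrhea, each with a grade 2 rule.

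Section 15.3 plans the number and percentage of treated subjects with AEs and a summary by type and severity. It does not mention the Section 11.a exclusions.

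**The concern.** The trial studies a two-drug regimen. A grade 1-2 event caused by azacitidine is toxicity of that regimen even when the attribution is right. When the attribution is wrong, an APR-246 effect is lost as well. The same symptom at the same grade is an AE in one patient and a non-event in another, depending on a chart note written by staff who know the treatment, in a trial with no control arm.

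At stake is the low-grade tolerability profile for the terms the protocol itself regards as characteristic of APR-246. A reader of the safety tables would take the nausea, dizziness and ataxia rows as complete for all grades, and nothing in Section 15.3 says otherwise.

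**Working it through.** The plan gives no figure to reproduce here. The check is a comparison of the text, followed by an illustration of size.

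**Step 1. Overlap of terms.**

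| Term | Excluded at grade 1-2 (Section 11.a) | APR-246 toxicity (Section 10.2 or Table 8) |
|---|---|---|
| Nausea | Named, azacitidine list | Section 10.2 and Table 8 |
| Dizziness | Named, transfusion list | Section 10.2 and Table 8 |
| Ataxia | Named, transfusion list | Table 8 |
| Vertigo | Not named; lists are open-ended | Section 10.2 |
| Dyskinesia | Not named; lists are open-ended | Table 8 |
| Vomiting, diarrhea | Not named; lists are open-ended | Table 8 |
| Injection site reactions, constipation | Named, azacitidine list | Not listed |
| Headache, fall | Named, transfusion list | Not listed in the visible text |

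Three terms are named on both sides. Four more could enter the exclusion because its lists are not closed.

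**Step 2. Whether the data are kept elsewhere in the trial database.** For these symptoms, largely not:

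- The study calendar notes (Section 13) keep physical examination and vital signs off the CRFs; findings reach the data only as AEs.
- The same notes keep concurrent medications off the CRFs, so use of an anti-emetic or antihistamine cannot stand in for the symptom.
- The internal safety review in Section 17.8 looks at events of grade 3 or above.
- Section 11.d has laboratory abnormalities graded and data collected on typical disease-related events. That softens the loss for blood counts, but not for nausea, dizziness or ataxia.

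**Step 3. Direction.** Let p be the true proportion of patients with a grade 1-2 event of a given term, and s the share of those patients whose every episode is charted to azacitidine or transfusion need. Then

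recorded proportion = p × (1 − s).

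This is never above p, and equals p only when s = 0.

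**Step 4. Size, by assumption only.** The documents give neither p nor s. For an illustration take the maximum accrual of 51 (Synopsis and Section 6), p = 30%, 50% or 70%, and s = 25%, 50% or 75%. At p = 50%, 51 × 0.50 = 25.5 patients have the event; with s = 50% the recorded proportion is 0.50 × (1 − 0.50) = 25%.

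| Assumed true p | Patients, 51 × p | s = 25% | s = 50% | s = 75% |
|---|---|---|---|---|
| 30% | 15.3 | 22.5% | 15% | 7.5% |
| 50% | 25.5 | 37.5% | 25% | 12.5% |
| 70% | 35.7 | 52.5% | 35% | 17.5% |

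Here s is a share of patients. If the same percentages were shares of events, the recorded patient proportion would be higher, because one episode not attributed away keeps the patient in the count.

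**The case against.** The case for leaving the text alone has real substance.

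- **The exclusion is conditional.** Without documented specific attribution, the event remains an AE. Section 17.8 provides for source data verification against medical records. A reader might infer that the attribution can never be checked; the documents do not support that, since a monitor can check it in the chart. What stands is that chart documentation does not put the event into the tables, and an analyst working from the database cannot see it.
- **Dose reductions.** A reader might infer that grade 2 events leading to an APR-246 reduction vanish from the AE tables. Section 10.5 applies Table 8 to toxicities suspected to be related to APR-246. An event that triggers a reduction is therefore suspected to be APR-246-related and cannot consistently be charted as specifically due to azacitidine or transfusion need. That inference fails.
- **Timing.** APR-246 runs on days 1-4 and azacitidine starts on day 4, after the infusion (Section 6.a). The Phase 1b lead-in has no azacitidine, so only the transfusion exclusion could apply there. Section 11.c names a temporal relationship as evidence of relatedness to the investigational product. This limits the room for misattribution. It does not help with events from day 4 onward, nor with correctly attributed azacitidine events, which are still toxicity of the combination.
- **Express exceptions.** A general definition followed by listed exceptions can be read as a disclosed choice of scope rather than a contradiction. That is fair, but a relatedness-free definition followed by an exclusion based on relatedness still needs reconciling, and Section 15.3 carries no caveat.
- **Headache and fall.** They appear in the exclusion list, but the visible text does not present them as APR-246 toxicities. They do not belong in the overlap.

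**Conclusion.** The point holds for low-grade events. Followed as written, the plan gives AE tables that under-count grade 1-2 toxicity of the combination for nausea, dizziness and ataxia, and possibly for vertigo, dyskinesia, vomiting and diarrhea. The direction follows from the text; the size does not. The percentages in the working rest on assumed rates and shares and should not be quoted as estimates.

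The reach is limited. Non-hematological DLTs are grade 3-4 events (Section 10.4), so a reader who inferred a biased dose-finding decision would go beyond the documents. Events of grade 3 or above, SAEs, events that trigger an APR-246 dose reduction, and the Phase 2 CR endpoint are likewise untouched. The change is worth making because it is cheap and the loss cannot be repaired from the database afterwards.

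**What to change.** Reconcile the definition and the exclusions in Section 11.a as follows:

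1. Record as AEs all grade 1-2 events whose terms the protocol itself lists as APR-246 toxicities: nausea, vomiting, diarrhea, dizziness, vertigo, ataxia and dyskinesia.
2. Record attribution to APR-246, to azacitidine and to transfusion need in three separate fields, so that attribution describes the event and no longer decides whether it is counted.
3. Keep the exclusion for terms that are clearly azacitidine-only, such as injection site reactions.
4. State any remaining exclusion in Section 15.3 and beside the safety tables. If data collection is already complete, this statement is the part that can still be done.

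The cost is some additional AE entry in at most 51 patients. No visits are added, and no dosing or clinical management rule changes.
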